## 1.0 Objectives / Specific Aims

### Specific Aim 1

The goal of Specific Aim 1 is to develop an effective remote mental health and substance use Screening, Brief Intervention and Referral to Treatment (SBIRT) program for pregnant and postpartum women. The **objectives** of this current application for Specific Aim 1 are to conduct a pilot RCT of a text-message based SBIRT and home-based telemedicine services for pregnant and postpartum women – called Listening to Women (LTW), compared to treatment as usual (TAU) with the primary objective to provide effect size estimates for a larger RCT.

**Specific Aim 1:** Conduct a pilot, small-scale randomized controlled trial to examine feasibility and preliminary efficacy of LTW, compared to TAU. Outcomes related to feasibility include percentage of eligible patients recruited, **study attrition**, **study retention**, and mental health and substance use treatment appointment attendance. Outcomes related to **preliminary efficacy** will include participation in screening, referral and treatment at baseline, compared to TAU.

The central hypotheses for Specific Aim 1 are that the study is feasible and women assigned to LTW will be more likely to screen positive and successfully obtain treatment in less time, compared to those that are assigned to TAU.

### Specific Aim 2

Upon completion of Specific Aim 1, the goal of Specific Aim 2 is to evaluate the effectiveness of a remote mental health and substance use Screening, Brief Intervention and Referral to Treatment (SBIRT) program for pregnant and postpartum women. The **objectives** of this current application for Specific Aim 2 are to conduct an RCT of a text-message based SBIRT and home-based telemedicine services for pregnant and postpartum women – called Listening to Women (LTW), compared to treatment as usual (TAU) with the primary objective to include attendance to treatment at baseline, compared to TAU.

**Specific Aim 2:** Conduct a randomized controlled trial to examine the effectiveness of LTW, compared to TAU. Outcomes related to **effectiveness** include attendance to treatment at baseline, compared to TAU.

The central hypotheses are that a greater proportion of women assigned to LTW will attend treatment following a referral, compared to TAU.

### Specific Aim 3

The goal of Specific Aim 3 is to gather data related to maternal and newborn diagnosis codes, health care utilization, and costs for our study participants with Medicaid.

**Specific Aim 3:** We will compare Medicaid data among those assigned to LTW vs. TAU.

The central hypothesis is that those assigned to LTW will have lower health care utilization and costs during the postpartum year, compared to TAU.

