To address these barriers we designed, implemented and piloted LTW in routine perinatal care in one obstetric practice (see 3.0 Intervention to be Studied) as part of a quality improvement project. Our pilot demonstrates high rates of participation with 87.78% (273/311) of women approached agreeing to take part in LTW and completing the text-message screening. Preliminary data comparing LTW (N=273) to a historical dataset extracted from the EHR including peripartum women receiving in-person SBIRT in the same clinic (N=2,988) found a significantly greater proportion of women enrolled in LTW screened positive (81.15% vs. 33.33%;  $\chi^2=169.50$ ,  $p<0.0001$ ), were referred for treatment (76.12% vs. 57.63%;  $\chi^2=18.03$ ,  $p<0.0001$ ), and received treatment (94.91% vs. 16.04%;  $\chi^2=245.41$ ,  $p<0.0001$ ), compared to women receiving in-person SBIRT.

While these preliminary data are exciting, a randomized control trial will be necessary to determine the feasibility and efficacy of LTW. The goal of Specific Aim 1 is to examine the feasibility and preliminary efficacy of the proposed RCT methodology. Specific Aim 1 will inform Specific Aim 2 to then conduct a larger-scale RCT that examines LTW, compared to a control condition. This will allow us to identify and address barriers in recruitment, retention, use of LTW, and other procedures essential to successful conduct of the RCT. This approach is consistent with expert recommendations to use pilot mechanisms to test the feasibility of doing a full-scale RCT, use data yielded by the pilot study to “de-bug” the methodology, and to assess optimal strategies to executing the RCT [51- R34].

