## **6.0 Number of Subjects**

A total of 450 participants will be randomized in Specific Aim 1 (n=100) and Specific Aim 2 (n=350). To randomize 450 participants we will need to approach about 1,500 participants in order to get to 450 total participants.

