## **10.0 Study Design / Methods**

Specific aim 1: A two arm pilot RCT (N=100) with 2:1 allocation will examine feasibility and preliminary efficacy of LTW, compared to TAU. Specific aim 2: A RCT (N=350) with 2:1 allocation will examine effectiveness of LTW, compared to TAU. As of the approval of amendment #12 the allocation will switch to 1(LTW):2(TAU) for specific aim 2. Recruitment will primarily occur proactively and remotely via the EHR. We will conduct a weekly EHR search via a recruitment report for all new pregnant and postpartum patients in the past week. The report will include mrn, age, race, ethnicity, date of prenatal care visit, date of postpartum visit, delivery date, ob/gyn provider name, MyChart account (Yes/No), cell phone number, email address and current ICD-9 or 10 diagnoses. Any patients who have not opted out of being contacted for research will be contacted and invited to participate. The study team will not cold-contact any patients who have chosen to opt-out of receiving contact about research or who have met the maximum number of contact attempts at the time of recruitment. If the potential participant has not opted out of being contacted, or the potential participant's provider has agreed to have the study team contact their patient, a phone call will be made or message will be sent via text, email or MyChart message to the potential participant inviting them to take part in the study. This invitation will include clear opt out procedures should the patient not wish to be contacted in the future for the purpose of this study. If interested, participants will complete a screening online via REDCap to determine study eligibility (see above for inclusion criteria). After completing preliminary determination of eligibility, if eligible and interested in participating in the study, participants will be scheduled for a time to complete informed consent (see 9.0 Consent Process).

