Statistical Analysis Plan

Sample Size and Power Analysis

Using a chi-square testing framework and a significance level of 0.05 and assuming two-sided hypothesis testing, both primary and secondary outcomes included a large enough sample size to detect differences between groups. Our a priori group sample sizes (usual care: n=191; LTWP: n=224) provided 80% power to detect between-group absolute differences in proportions ranging from 6% to 12% in the primary study outcomes (for example, screened: 65.2% [usual care] versus 77.7% [LTWP]; screened positive: 21.7% versus 34.2%, respectively; referred: 12.5% versus 23.1%, respectively; and attended treatment: 2.1% versus 8.3%, respectively). Our group sample sizes among participants completing a screen (usual care: n=63; LTWP: n=221) provided 80% power to detect between-group absolute differences in proportions ranging from 11% to 18% in the secondary study outcomes (for example, screened positive: 17.5% [usual care] versus 35.4% [LTWP]; referred: 3.2% versus 15.3%, respectively; and attended treatment: 1.6% versus 12.3%, respectively). The usual care rates used in these calculations were based on data published from earlier work on the LTWP program.

Data Analysis

We will assess the adequacy of randomization by comparing LTWP versus usual care (UC) on demographic, obstetric, and psychiatric baseline characteristics, using t-tests or Wilcoxon rank sum tests for continuous variables and chi-square tests or Fisher's exact tests for categorical variables, respectively. Descriptive statistics will be calculated for each screening method (LTWP versus usual care), including counts and percentages for participants who were screened, screened positive, referred to treatment, and attended treatment. Unadjusted differences in outcomes between people assigned to LTWP versus UC will be calculated using chi-square tests because all study outcomes are dichotomous. Relative risk (RR) ratios will be estimated and reported along with their 95% confidence intervals. All hypothesis tests will be two-sided with a type 1 error set at 0.05, and all analyses will be performed using SAS statistical software, version 9.4 (Cary, NC).

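### At 100 women, Aim 1's effect-size estimates are too imprecise to plan from at the SAP's illustrative rates, and the relative risk alone may be undefined for attendance

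*Protocol*

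**What the plan says.** Protocol 1.0 describes Aim 1 as a pilot trial "with the primary objective to provide effect size estimates for a larger RCT", and the protocol summary in section 12.0 repeats this. Section 10.0 gives the size: "A two arm pilot RCT (N=100) with 2:1 allocation will examine feasibility and preliminary efficacy of LTW, compared to TAU". The direction of the ratio is not printed there. It can be inferred as two LTW to one usual care, because the same section says that from amendment 12 "the allocation will switch to 1(LTW):2(TAU) for specific aim 2".

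Section 2.0 links the two stages: "Specific Aim 1 will inform Specific Aim 2 to then conduct a larger-scale RCT that examines LTW, compared to a control condition". Section 6.0 puts 100 women in Aim 1 and 350 in Aim 2. It gives no derivation for either number and no rule for revising the second after the first.

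The SAP does not separate the aims. Its power statement uses "a significance level of 0.05 and assuming two-sided hypothesis testing", groups of 191 usual care and 224 LTW (415 in all), and absolute differences in proportions. On the source of its inputs it says: "The usual care rates used in these calculations were based on data published from earlier work on the LTWP program". Under Data Analysis the effect measure is the relative risk: "Relative risk (RR) ratios will be estimated and reported along with their 95% confidence intervals". No risk difference is planned, and nothing is said about an arm with no events.

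**The concern.** An objective framed as effect-size estimation asks for precision, and no precision target or justification for 100 women appears. If the effects are of the order that the SAP uses to illustrate its power, a pilot of this size returns intervals that include both no effect and effects about twice as large. A sample size or a decision built on the point estimate alone would then rest mostly on chance.

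The second problem concerns the scale. Treatment attendance, the primary outcome of Aim 2, is the rarest step of the cascade in usual care. A relative risk has the usual-care proportion in its denominator, so with no usual-care attenders it does not exist. The SAP would then have no effect estimate to report for that outcome. Since power is stated in absolute differences and results are to be given as ratios, a reader also cannot set the results directly against the plan.

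**Working it through.** **Inputs.** Aim 1 size and ratio: Protocol 10.0, 100 at 2:1, hence 33 usual care and 67 LTW (derived). Rates, usual care versus LTW, from the SAP: screened 65.2% v 77.7%; screened positive 21.7% v 34.2%; referred 12.5% v 23.1%; attended 2.1% v 8.3%. The SAP offers these as examples of detectable differences.

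**Step 1: reproduce the SAP's 80%.** Two-sided chi-square at 0.05, pooled variance under the null, no continuity correction:

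power = Φ[(|p2 − p1| − 1.96·SE0) / SE1]

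For attendance with 191 and 224:
- pooled proportion = (191×0.021 + 224×0.083)/415 = 0.0545
- SE0 = √[0.0545×0.9455×(1/191 + 1/224)] = 0.0224
- SE1 = √[0.021×0.979/191 + 0.083×0.917/224] = 0.0212
- power = Φ(0.86) = 80.5%

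The other three give 80.6% (screened), 80.8% (screened positive) and 80.3% (referred). The SAP's figure reproduces.

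**Step 2: the same rates at 33 and 67.** Half-width = 1.96·√[p1(1 − p1)/33 + p2(1 − p2)/67]. For attendance: 1.96·√(0.000623 + 0.001136) = 8.2 points. Relative-risk intervals are on the log scale.

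| Outcome | Difference (points) | 95% half-width | 95% CI | RR (95% CI) | Power |
|---|---|---|---|---|---|
| Screened | 12.5 | 19.1 | −6.6 to 31.6 | 1.19 (0.90 to 1.58) | 27% |
| Screened positive | 12.5 | 18.1 | −5.6 to 30.6 | 1.58 (0.76 to 3.26) | 24% |
| Referred | 10.6 | 15.1 | −4.5 to 25.7 | 1.85 (0.68 to 5.04) | 22% |
| Attended | 6.2 | 8.2 | −2.0 to 14.4 | 3.95 (0.34 to 46) | 18% |

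Every half-width exceeds its difference. A 50:50 split hardly changes this (17.5, 17.4, 14.8 and 8.6 points), so the limits are the total of 100 and the low event rate, not the 2:1 ratio.

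**Step 3: chance of no usual-care attenders**, (1 − p)^n:
- Aim 1 at the SAP rate: expected events 33×0.021 = 0.7; 0.979^33 = 50%
- Aim 1 at an assumed 5%: 0.95^33 = 18%
- Aim 1 at an assumed 10%: 0.90^33 = 3%
- SAP secondary set: expected events 63×0.016 = 1.0; 0.984^63 = 36%
- SAP full set: 0.979^191 = 1.7%

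For the other pilot outcomes the chance is 1.2% (referred) and below 0.1% (screened positive, screened).

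**Step 4: a much larger effect.** Section 2.0 reports a non-randomised comparison with historical records: screened positive 81.15% v 33.33%. With 67 and 33 women that is a difference of 47.8 points, half-width 18.6, power above 99%. For attendance, if the three percentages are read as nested steps (my assumption), usual care is 0.3333×0.5763×0.1604 = 3.1% and LTW is 0.8115×0.7612×0.9491 = 58.6%. The difference is 55.5 points, half-width 13.2, but the RR is 19 (2.8 to 130). The chance of no usual-care attenders is still 0.969^33, about 36%, because it depends only on the usual-care rate.

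**Step 5: does a risk difference solve the zero case?** With 0 of 33 and 6 of 67 attending, the RR is undefined. The Newcombe interval gives 9.0 points (−2.5 to 18.2). With 1 of 33 and 6 of 67 it gives 5.9 points (−7.3 to 15.5). Both can be reported and read against the power statement.

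**The case against.** The strongest reply is that the SAP's rates are detectable differences, not forecasts. If the LTW rates were chosen to give 80% power at 415, power of 18% to 27% at 100 is close to automatic. This stands: the intervals above show what the pilot would yield if effects were of that order, not what it will yield. Effects like those in section 2.0 would be seen clearly, although that comparison is non-randomised.

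The zero-event problem is also narrow. It bites for attendance only, and it depends on the usual-care rate. Section 8.0 says that diagnosis codes are used to approach enough women likely to screen positive, which could raise that rate. At an assumed 10% the problem nearly disappears in the pilot. It remains at the SAP's own rates, in the secondary set as well.

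A reader might infer that Aim 2's 350 was taken from other data and that the pilot estimates go unused. The documents do not say so. Only the SAP's usual-care rates are attributed to earlier work, and that calculation is for 415. At the SAP's attendance rates, 350 gives about 64% power at 2:1 and 74% at 1:2, so 350 does not come from it. The usual-care inputs do look like section 2.0's historical rates (65.2%×33.33% = 21.7%, ×57.63% = 12.5%, ×16.04% = 2.0%, against a printed 2.1%), but that is inference and concerns the 415. An amended protocol would print 350 whether or not pilot results shaped it.

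Finally, small pilots are normal for feasibility work, and nothing here touches Aim 1's feasibility outcomes.

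**Conclusion.** The point holds as one about precision and reporting. At the SAP's illustrative rates, and with 33 usual-care and 67 LTW women, the Aim 1 estimates have 95% half-widths of about 1.3 to 1.5 times the differences (8.2/6.2 to 19.1/12.5). They are too imprecise on their own to plan a trial. For attendance, the SAP's only effect measure is undefined in about half of such pilots at 2.1% usual-care attendance, 18% at 5%, and about 36% of the time in the SAP's secondary set. The basis for 350 is unstated, and no rule links it to pilot results.

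It would go too far to say that the objective cannot be delivered: a risk difference can always be computed, and large effects would be detectable. A range of trial sizes implied by simulated pilots would also mislead, since its upper end depends on how the roughly 9% of pilots with a null or reversed attendance effect are counted.

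The conclusion rests on the derived 33:67 split, the SAP's rates, and Wald intervals for the half-widths.

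**What to change.** In the SAP, Data Analysis, add that for every dichotomous outcome the risk difference will be reported with a Newcombe or Miettinen-Nurminen 95% confidence interval beside the relative risk. This puts results on the scale of the power statement and stays defined when an arm has no events.

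Add a sentence that any results from Aim 1 alone will be given for all randomised women, as estimates with these intervals, and that they are too imprecise by themselves to size or justify a larger trial.

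The cost is two or three sentences and a few more table columns. Sample size, procedures and data collection do not change. A line in Protocol 6.0 giving the basis for 350 would close the remaining gap.

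Re-labelling Aim 1's primary objective as feasibility is optional. It would need matching edits in section 4.0, which lists efficacy outcomes as primary and feasibility outcomes as secondary for the pilot. It may also be retrospective, since amendments 10 and 12 suggest that Aim 2 is already under way.

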## 2.0 Background

During pregnancy and the year postpartum (perinatal period), mental health problems are common such as mood, anxiety and substance use disorders. Perinatal mood and anxiety disorders are the most common complication of pregnancy and childbirth affecting at least 1 in 7 perinatal women [1]. Perinatal substance use is also common, and the prevalence is increasing. Perinatal opioid use disorder alone has increased 4-fold over the past decade [2]. Perinatal mental health and substance use are associated with significant maternal, obstetric, infant and child morbidity [3-9], and mortality [10-14].

Given the prevalence and impact of perinatal mood, anxiety and substance use disorders, and evidence demonstrating mitigation of its effects on maternal and child health through psychotherapy and psychopharmacotherapy [16,17], a multitude of professional societies recommend universal screening of pregnant and/or postpartum women using validated screening tools and provision of adequate mental health treatment and/or treatment referrals [18-22]. Unfortunately, however, the vast majority of women with mood, anxiety or substance use problems will remain under-diagnosed and under-treated [23-24]. Less than 50% of peripartum women with a mental illness, and less than 20% of women with a substance use problem are identified in clinical settings [6]. Among these women, less than 15% receive treatment, fewer than 10% receive adequate treatment and less than 5% achieve remission [4].

While mental health screening is widely accepted by perinatal women and Ob/Gyn providers [25,26], further work is needed to facilitate implementation of screenings in Ob/Gyn practices that translate to treatment participation. However, key provider and systems-level barriers to treatment exist and include: 1) lack of screening in obstetric settings and lack of provider training in technical aspects of mental health and substance use disorder care [26-28] and relevant communication skills [29]; 2) absence of standardized processes and procedures for integrated obstetric and mental health and substance use disorder treatment [29,30]; 3) lack of mental health providers willing to treat pregnant women [30]; 4) lack of referral networks [29-33]; and, 5) inadequate capacity and resources to ensure mental health evaluation, treatment, follow-up, and care coordination [29- 35].

To address these barriers we designed, implemented and piloted LTW in routine perinatal care in one obstetric practice (see 3.0 Intervention to be Studied) as part of a quality improvement project. Our pilot demonstrates high rates of participation with 87.78% (273/311) of women approached agreeing to take part in LTW and completing the text-message screening. Preliminary data comparing LTW (N=273) to a historical dataset extracted from the EHR including peripartum women receiving in-person SBIRT in the same clinic (N=2,988) found a significantly greater proportion of women enrolled in LTW screened positive (81.15% vs. 33.33%;  $\chi^2=169.50$ ,  $p<0.0001$ ), were referred for treatment (76.12% vs. 57.63%;  $\chi^2=18.03$ ,  $p<0.0001$ ), and received treatment (94.91% vs. 16.04%;  $\chi^2=245.41$ ,  $p<0.0001$ ), compared to women receiving in-person SBIRT.

While these preliminary data are exciting, a randomized control trial will be necessary to determine the feasibility and efficacy of LTW. The goal of Specific Aim 1 is to examine the feasibility and preliminary efficacy of the proposed RCT methodology. Specific Aim 1 will inform Specific Aim 2 to then conduct a larger-scale RCT that examines LTW, compared to a control condition. This will allow us to identify and address barriers in recruitment, retention, use of LTW, and other procedures essential to successful conduct of the RCT. This approach is consistent with expert recommendations to use pilot mechanisms to test the feasibility of doing a full-scale RCT, use data yielded by the pilot study to “de-bug” the methodology, and to assess optimal strategies to executing the RCT [51- R34].

## 3.0 Intervention to be studied

LTW is a mobile phone-based program designed to enhance delivery of Screening, Brief Intervention, and Referral to Treatment (SBIRT), an evidence-based approach for mental health and substance use screening

and treatment for perinatal women [36-38]. This program was created as a result of key informant interviews with obstetric providers and pregnant and postpartum women with opioid use disorders. Feedback from these groups informed the development of LTW.

The program utilizes mobile phone text message-based screenings with immediate automated feedback, paired with remote care coordination and, if appropriate, home-based telemedicine mental health and substance use disorder treatment services. Women coming into routine prenatal care (see Recruitment) are eligible to take part in the study. Those agreeing to take part are sent a text message with routine mental health and substance use screening questions (see LTW protocol for screening questions) currently employed as part of standard of care. These screening questions are the SBIRT which is a survey with 9 questions related to depression, anxiety, substance abuse (alcohol, cigarettes, other drugs including prescription medication), and domestic violence (see LTW protocol). However, LTW uses text-message based screening with phone based assessment and referral to treatment, and TAU is an in-person screening and referral to treatment assessment. The same screening tools are used to assess substance abuse and mental health problems in LTW and TAU. Once they complete these screenings via text message, they are provided immediate feedback about their scores, and recommendations (see LTW protocol for automated messages). Contact information for the study's care coordinator is also provided along with her availability i.e., Monday – Friday 8am-5pm. In addition, while specific questions about suicidal ideation are not asked via the text message screening, all participants receive a text message: "If you are ever experiencing a mental health emergency, such as a desire to harm yourself or others, please go to your nearest emergency room. If you are feeling suicidal you can call the National Suicide Prevention Lifeline [name] anytime" (see LTW protocol for automated messages).

Information about the screening is stored in a REDCap database. A care coordinator is reviewing this information Monday through Friday 8am-5pm and texts or calls any patient that screens positive for mental health or substance use that requires further assessment as would be done in-person during routine clinical care (see LTW protocol describing branching logic from screens and clinical risk categories). The care coordinator contacts the patient and further assesses their mental health and substance use symptoms and needs for resources and/or treatment. If the participant would benefit from further mental health and/or substance use evaluation and treatment, the care coordinator schedules the patient for a home-based telemedicine visit. The care coordinator communicates all screening information in the Electronic Health Record (EHR) for all providers to review, and if applicable includes information about the scheduled appointment or resources provided.

